### **6.3.5 Columbia–Suicide Severity Rating Scale**

The C-SSRS monitors changes in suicidal thinking and behavior over time, in order to determine risk ([Posner et al. 2011](#)). The following four constructs are measured: the severity of ideation, the intensity of ideation, behavior, and lethality.

For subjects who completed the Baseline/Screening version in Study ACP-103-054 or Study ACP-103-059, the Since Last Visit version will be administered at all visits. The C-SSRS results for each subject should be reviewed by the Investigator at each visit. If at any time the C-SSRS results for a given subject reveal potential suicidality, then the Investigator should assess the clinical significance of such results. If a clinically significant risk of suicidality is identified for a subject, then the Investigator should discontinue the subject and implement appropriate treatment ([Section 4.4](#)).

### **6.3.6 Extrapyramidal Symptom Rating Scale–Abbreviated**

The ESRS ([Chouinard and Margolese 2005](#)) was developed to assess drug induced movement disorders such as parkinsonism, akathisia, dystonia and tardive dyskinesia with established reliability, validity, and sensitivity. It consists of a questionnaire of parkinsonian symptoms, physician examination of parkinsonism, dyskinetic movements, and global impression of tardive dyskinesia. The ESRS-A, an accepted modified form of the original ESRS, will be used during the study to monitor for any worsening in extrapyramidal symptoms or signs at all scheduled and unscheduled visits.

### **6.3.7 Laboratory Evaluations**

Clinical laboratory sample collection is encouraged, but not required to be completed under fasting conditions. The laboratory evaluations will include, but are not limited to, the following:

- Clinical chemistry serum tests

- Sodium (Na), potassium (K), chloride (Cl), phosphorus (P), calcium (Ca), carbon dioxide (CO2), blood urea nitrogen (BUN), creatinine (CR), uric acid
- Alanine aminotransferase (ALT), aspartate aminotransferase (AST), gamma-glutamyl transpeptidase (GGT), alkaline phosphatase (ALP), total bilirubin (TBIL), lactate dehydrogenase (LDH)
- Glucose
- Albumin (ALB), total protein
- Prolactin
- Creatine kinase (CK)/creatinine phosphokinase (CPK)
- Lipid panel
  - Total cholesterol, HDL-cholesterol, triglycerides, LDL-cholesterol, very low density lipoprotein cholesterol
- Pregnancy test
  - A urine pregnancy test should be performed at all designated visits ([Table 6–1](#)) for women of child-bearing potential
    - If urine cannot be obtained in women of childbearing potential, a serum pregnancy test should be done in its place
- Hematology tests
  - Complete blood count (CBC) including:
    - White blood cell (WBC) count
    - Complete differential (relative and absolute)
    - Hematocrit (Hct), hemoglobin, red blood cells (RBC), platelets
    - Reticulocyte count
- Urinalysis
  - Blood, RBCs, WBCs, protein, glucose, ketones, specific gravity, pH
  - Reasonable efforts should be made to collect a urine sample from all subjects
- Urine toxicity (drug) screen
  - Urine toxicity (drug) screen will test for controlled substances
  - Sites will be supplied with instant-read dipstick urine toxicity (drug) screen tests to utilize as a tool at the Baseline visit in order to determine if the subject continues to meet eligibility. This test will not take the place of the urine toxicity (drug) screening performed by the central laboratory.

- Subjects who test positive in the urine toxicity (drug) screen performed by the central laboratory for benzodiazepines, opiates, any other controlled medication, tetrahydrocannabinol (THC), or illicit substance, will be withdrawn from the study unless any prohibited medication or substance has been discontinued and withdrawal from the study presents an unacceptable medical risk for the subject. The justification to allow the subject to continue in the trial will be made by the Sponsor/Medical Monitor, with medical input from the Investigator, and will be documented. If a subject is allowed to remain in the trial, this will be reported as a major protocol deviation, not a waiver. In addition, restrictions listed in [Appendix A](#) should be followed.
- Reasonable efforts should be made to collect a urine sample at applicable scheduled visits as described in “Urinalysis” above

Laboratory evaluations will be completed according to the schedule presented in Table 6–1 and procedures detailed in the study laboratory manual. Additional safety testing may be performed at the discretion of the Investigator or designee.

**Table 6–1 Safety Laboratory Evaluations**

Visit	Tests
Visit 1 (Baseline)	CHEM, CBC, UA, urine toxicity (drug) screen, and urine pregnancy test a
Visit 5 (Week 12) and Visit 9 (EOT/ET)	CHEM, CBC, UA, urine toxicity (drug) screen, and urine pregnancy test a
Visits 3, 4, 6, 7, 8	Urine pregnancy test a

Abbreviations: CBC=complete blood count; CHEM=clinical chemistry serum tests; EOT=end of treatment; ET=early termination; UA=urinalysis

a To be completed only if female is of childbearing potential. If urine cannot be obtained in women of childbearing potential, a serum pregnancy test should be done in its place.

### 6.3.8 Impact of COVID-19 Pandemic on Safety Assessments

Subjects who cannot attend clinic visits due to the COVID-19 pandemic are allowed to participate in remote visits via telephone or video, or site staff can visit subjects in their homes.

Some safety assessments may not be able to be performed, or may be performed under different circumstances, due to the subject not being able to come to the clinic. Modifications and accommodations for safety assessments in the context of remote visits are described briefly below.

#### **6.3.8.1 Priority Medical Assessments in Remote Visits**

The C-SSRS is to be performed as a priority, along with an assessment of AEs and COVID-19 symptoms. Additionally, subjects are to be queried about concomitant medications, and their background antidepressant and IP compliance.

#### **6.3.8.2 Physical Examinations, Vital Signs, Height, and Weight**

Physical examinations, vitals, height, and weight may not be able to be performed because the visit has to be conducted remotely. If the visit is remote, the subject may report vitals obtained on home devices. If vitals are obtained outside of the investigator site, this should be documented in the source record.

#### **6.3.8.3 Electrocardiograms**

ECGs may have to be performed by site staff during a home visit after discussion with Medical Monitor. In the US and UK, a 6-lead ECG device will be given to subjects in order to perform ECGs on themselves at home when they cannot go to the clinic and site staff cannot go to their home. This should be done in discussion with the Medical Monitor. When an ECG is performed outside of the investigator site, this should be documented in the source record.

#### **6.3.8.4 Columbia-Suicide Severity Rating Scale**

See Section 6.3.8.1 above.

#### **6.3.8.5 Extrapyramidal Symptom Rating Scale-Abbreviated**

When the ESRS-A motor examination cannot be performed (e.g., when the visit is performed via telephone with no video component) then no scoring of symptoms is to be completed. The clinical interview questions are to be asked for all symptom areas in order to obtain information about the presence and severity of involuntary movements experienced by the patient and this is to be documented in the source record. The clinical significance of any symptoms is to be evaluated by the Investigator, and the adverse event page updated when new or worsening symptoms are reported.

#### **6.3.8.6 Laboratory Evaluations**

If subjects cannot attend clinic visits for laboratory evaluations, they are allowed to use local laboratories, or to have site staff visit them at their homes for blood draws.

### **6.4 Safety Follow-up**

A 30-day safety follow-up telephone contact is to be completed for subjects who complete the treatment period of the study, as well as those who discontinue prematurely from the

study. Subjects should have the following completed at least 30 days after last dose of study drug:

- Assessment of concomitant medications/treatments
- Assessment of AEs

## **6.5 Unscheduled Visits**

Unscheduled visits may occur as determined by the Investigator. The following safety assessments generally should be recorded at each unscheduled visit: assessment of AEs, assessment of concomitant medications/treatments, measurement of vital signs and weight, ESRS-A, and C-SSRS. The Investigator may perform any additional safety evaluations deemed by the Investigator to be clinically indicated. Study drug may be dispensed to the subject at unscheduled visits if needed.

### **6.5.1 Impact of COVID-19 on Unscheduled Visits**

If a subject cannot attend the clinic for an unscheduled visit, this may occur remotely or by site staff visit to the subject's home.

## **7 ADVERSE EVENTS**

### **7.1 Specification of Safety Parameters**

#### **7.1.1 Definition of Adverse Event**

An AE is defined as “any untoward medical occurrence in a patient or clinical study participant, temporally associated with the use of study drug, whether or not considered related to study drug”.

An AE can therefore be any unfavorable and unintended sign (e.g., an abnormal laboratory finding), symptom, or disease temporally associated with the use of a drug, without any judgment about causality or seriousness. An AE can arise from any use of the drug (e.g., off-label use, use in combination with another drug) and from any route of administration, formulation, or dose, including an overdose.

A suspected adverse reaction is any AE for which there is a reasonable possibility that the drug caused the AE.

AEs do not include the following:

- Stable or intermittent chronic conditions (such as myopia requiring eyeglasses) that are present prior to Baseline and do not worsen during the study

- Medical or surgical procedures (e.g., surgery, endoscopy, tooth extraction, transfusion). The condition that leads to the procedure is an AE if not present at Baseline.
- Overdose of concomitant medication without any signs or symptoms unless the subject is hospitalized for observation
- Hospitalization for elective surgery planned prior to study (situation where an untoward medical occurrence has not occurred)
- Pregnancy will not be considered an AE, but if it occurs, it will be reported on a pregnancy form

### 7.1.2 Definition of Serious Adverse Event

In addition to the severity rating, each AE will be classified by the Investigator as “serious” or “not serious.” The seriousness of an event will be defined according to the applicable regulations and generally refers to the outcome of an event. An SAE is one that meets one or more of the following:

- Is fatal
- Is immediately life threatening
- Results in disability or permanent damage
- Requires hospitalization
- Prolongs existing hospitalization
- Is a congenital anomaly or birth defect (in an offspring)
- Is medically significant

### Definition of Life Threatening

A life-threatening event places the subject at immediate risk of death from the event as it occurred. This does not include an AE, which, had it occurred in a more severe form, might have caused death.

### Definition of Hospitalization

Hospitalization is defined by the Sponsor as a full admission to the hospital for diagnosis and treatment. This includes prolongation of an existing inpatient hospitalization.

Examples of visits to a hospital facility that do **not** meet the serious criteria for hospitalization include:

- Emergency room visits (that do not result in a full hospital admission)
- Outpatient surgery

- Preplanned or elective procedures
- Protocol procedures
- Social hospitalization, defined as admission to the hospital as a result of inadequate family support or care at the subject's primary residence

### **Definition of Disability or Permanent Damage**

Disability is defined as a persistent or significant incapacity or substantial disruption of the ability to conduct normal life functions.

### **Definition of Medically Significant**

Important medical events (medically significant events) that may not result in death, be life threatening, or require hospitalization may be considered to be an SAE when, based upon appropriate medical judgment, they may jeopardize the subject or may require medical or surgical intervention to prevent one of the outcomes listed in this definition. Examples of such events are intensive treatment in an emergency room or at home for allergic bronchospasm, blood dyscrasias, or convulsions that do not result in hospitalization or development of drug dependency or drug abuse.

An SAE may also include any other event that the Investigator or Medical Monitor judges to be serious or that suggests a significant hazard, contraindication, side effect, or precaution.

## **7.2 Classification of an Adverse Event**

### **7.2.1 Severity of Event**

The severity of each AE will be graded on a 3-point scale and reported in detail as indicated on the eCRF:

- **Mild:** awareness of sign or symptom but easily tolerated, causing minimal discomfort, and not interfering with normal everyday activities
- **Moderate:** sufficiently discomforting to interfere with normal everyday activities
- **Severe:** incapacitating and/or preventing normal everyday activities

### **7.2.2 Relationship to Study Drug**

The causality of each AE should be assessed and classified by the Investigator as "related" or "not related." An event is considered related if there is a reasonable possibility that the event may have been caused by the product under investigation (i.e., there are facts, evidence, or arguments to suggest possible causation).

#### **Consider the following when assessing causality:**

- Temporal associations between the agent and the event

- Response to cessation (de-challenge) or re-challenge
- Compatibility with known class effect
- Known effects of concomitant medications
- Pre-existing risk factors
- A plausible mechanism
- Concurrent illnesses

#### 7.2.2.1 Duration

The start and stop dates for AEs will be recorded using the following criteria:

- **Start:** Date of the first episode of the AE or date of significant sustained worsening in severity
- **Stop:** Date when AE either ceased permanently or changed in severity

#### 7.2.2.2 Frequency

The frequency of the AE should be indicated according to the following definitions:

- **Single:** Experienced once, without recurrence
- **Recurrent:** More than one discrete episode with the same severity

#### 7.2.2.3 Action Taken with Study Drug

- **Dose not changed:** No change in study drug
- **Drug interrupted:** Study drug temporarily stopped
- **Drug withdrawn:** Study drug discontinued permanently

#### 7.2.2.4 Therapy

- **None:** No new treatment instituted
- **Medication:** New treatment initiated as a direct result of AE
- **Other:** Other action required

#### 7.2.2.5 Outcome

- **Recovered/resolved:** Recovered or resolved
- **Recovered/resolved with sequelae:** Recovered or resolved with sequelae
- **Not recovered/not resolved:** Not recovered or not resolved
- **Fatal:** Death due to an AE
- **Unknown:** Unknown

#### **7.2.2.6 Seriousness**

- **Not serious**
- **Serious**

#### **7.2.3 Definition of Unexpectedness**

An AE, the nature or severity of which is not consistent with the information provided in the Reference Safety Information section of the current pimavanserin Investigator's brochure.

#### **7.3 Time Period and Frequency for Event Assessment and Follow-up**

Adverse events with an onset before the first dose of open-label pimavanserin in the present study will be recorded as an AE in the antecedent study. All ongoing AEs from Study ACP-103-054 and Study ACP-103-059 will be carried over after informed consent has been obtained for the present study and recorded from Baseline for the present study until resolution or the follow-up safety assessment. An adverse event occurring after the first dose of open-label pimavanserin in the present study will be recorded as an AE in the present study. Adverse events for the present study will be recorded from the time of first dose of open-label pimavanserin through the study safety follow-up period.

All AEs must be either resolved or stable at the end of the study safety follow-up period of the present study. If ongoing at the end of the study safety follow-up period, the subject should be referred for appropriate treatment.

In the event that a subject discontinues and has an ongoing AE at the time of discontinuation ([Section 4.4.1](#)) or is withdrawn from the study because of an AE, the subject should be followed and treated by the Investigator until the AE has resolved, stabilized, or a new chronic baseline has been established.

#### **7.4 Reporting Procedures**

##### **7.4.1 Adverse Event Reporting**

The Investigator must record all observed AEs and all reported AEs. At each visit, the Investigator should ask the subject a nonspecific question (e.g., "Have you noticed anything different since your last visit?") to assess whether any AEs have been experienced since the last report or visit.

Note that any use of medication (and specifically any newly prescribed medication) during the course of a study may indicate the occurrence of an AE that may need to be recorded on both the AE and the concomitant medication page.

All AEs, serious and not serious, will be recorded on the AE eCRF page using appropriate medical terminology. Severity and relationship to study drug will be assessed by the Investigator.

When possible, clinical AEs should be described by diagnosis and not by symptoms (e.g., “cold” or “seasonal allergies” instead of “runny nose”).

All AEs, *whether or not related to the study drug*, must be fully and completely documented on the AE eCRF and in the subject’s notes.

#### **7.4.2 Serious Adverse Event Reporting**

The reporting of SAEs by the Sponsor or designee to the regulatory authorities is a regulatory requirement. Each regulatory authority has established a timetable for reporting SAEs based upon established criteria.

Serious AEs must be reported within 24 hours of discovery to the Sponsor or its designee; use the appropriate form for initial and/or follow-up reporting.

At a minimum, events identified by the Sponsor to require expedited reporting as serious, unexpected, and related to study drug must be brought to the attention of the responsible institutional review board/ethics committee (IRB/EC), as per applicable regulations. These will be provided by the Sponsor after their assessment. For European Union member states, the Sponsor or its designee will provide reports of suspected unexpected serious adverse reactions (SUSARs) directly to the ECs, as required by local legislation. In all other countries, it is the Investigator’s responsibility to provide these expedited reports to the responsible IRB/EC. It is also the Investigator’s responsibility to notify the responsible IRB/EC regarding any new and significant safety information.

When an SAE occurs, Investigators will review all documentation related to the event and will complete the paper SAE form (for initial and/or follow-up information) and fax or email (within 24 hours of discovery) to the contact information provided on the SAE form.

Subjects will be followed through the safety follow-up period for 30 days after last dose of study drug for any SAEs and/or other reportable information until such events have resolved or the Investigator, in conjunction with the Sponsor, deems them to be chronic or stable.

In the event of any SAE (other than death), the study subject will be instructed to contact the Investigator (or designee) using the telephone number provided in the ICF. All subjects experiencing an SAE will be seen by the Investigator or designee as soon as is feasible following the report of the SAE.

Serious AEs occurring after the study follow-up period of 30 days after last dose of study drug should be reported if in the judgment of the Investigator there is “a reasonable possibility” that the event may have been caused by the product.

SAEs should also be reported to the IRB/EC according to local regulations.

### **7.4.3 Reporting of Pregnancy**

Any female subject who becomes pregnant during the study (with or without AEs) must be withdrawn from the study and the pregnancy must be reported on the Pregnancy form within 24 hours of discovery to the Sponsor or its designee. Any female subject who becomes pregnant during the study will be followed through the pregnancy outcome.

Any AEs that are the consequence of pregnancy and which meet the criteria for serious should also be reported via the SAE form.

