### **3 STUDY DESCRIPTION**

#### **3.1 Overview of Study Design**

This study will be a 52-week open-label extension study to evaluate the long-term safety and tolerability of pimavanserin in subjects with major depressive disorder and inadequate response to antidepressant treatment. Up to approximately 80 sites will participate in this study. The total duration of exposure to pimavanserin may be greater than 52 weeks (e.g., up to 58 weeks) as subjects may have been treated with pimavanserin in the antecedent studies, ACP-103-054 and ACP-103-059. The duration of participation for individual study subjects will be up to approximately 56 weeks.

The study will have two periods ([Figure S-1](#)):

- Open-label treatment period (52 weeks)
- Safety follow-up period (at least 30 days)

The end of treatment (EOT) visit for the antecedent study, Study ACP-103-054 or Study ACP-103-059, is the Baseline visit for the present study.

Subject consent for the present study must be obtained prior to the final procedures being performed at the antecedent study's (ACP-103-054 or ACP-103-059) end of treatment (EOT) visit. Data from the EOT procedures of Studies ACP-103-054 and ACP-103-059 will be carried over to the ACP-103-055 study to be included as baseline information for the present study and this visit will be considered Baseline (Visit 1).

The study completion date (or when a subject is considered to have completed the study) is defined as the date the final subject, across all sites, completes their final protocol-defined assessment. Please note that this includes the safety follow-up visit/contact, whichever is later. Procedures for when a subject is lost to follow-up are provided in [Section 4.5](#).

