### **4.1 Inclusion Criteria**

A subject must meet all of the following inclusion criteria to be eligible for participation in the study.

1. Completed the antecedent study, Study ACP-103-054 or Study ACP-103-059
2. May benefit from longer term therapy with open-label pimavanserin treatment in the judgment of the Investigator
3. Is willing and able to provide informed consent. Consent for the present study **must be** obtained prior to the procedures being performed at the Week 6/EOT visit of Study ACP-103-054 or Study ACP-103-059

4. Is capable of communicating with the site personnel, able to complete subject-reported outcome measures and can be reliably rated on assessment scales (in the opinion of the Investigator)
5. If the subject is female, she must not be pregnant or breastfeeding. She must also be of non-childbearing potential (defined as either surgically sterilized or at least 1 year postmenopausal) OR must agree to use TWO clinically acceptable methods of contraception during the study and 1 month following completion of the study.

Acceptable methods of contraception include the following:

- a. A barrier method (condom, diaphragm, or cervical cap) with spermicide
- b. Hormonal contraception, including oral, injectable, transdermal, or implantable methods
- c. Intrauterine device (IUD)

Only one of the two clinically acceptable methods can be a hormonal method.

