#### **7.4.3.1 Reporting Paternal Drug Exposure**

Paternal drug exposure is defined as a father’s exposure to a medicinal product before or during his partner’s pregnancy. Any paternal drug exposure cases must be reported to the Sponsor within 24 hours of discovery via the Pregnancy form. Any AEs that are the consequence of paternal drug exposure and which meet the criteria for serious must also be reported to the Sponsor within 24 hours of discovery via the SAE form.

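### Pregnancies conceived late in dosing or in the 30 days afterwards are reportable but may go undetected, and the female reporting window does not match the contraception period

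*Protocol*

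**What the plan says.** **Reporting rule.** Protocol 7.4.3 states: "Any female subject who becomes pregnant during the study (with or without AEs) must be withdrawn from the study". The Pregnancy form is due within 24 hours of discovery. Outcome follow-up has the same limit: "Any female subject who becomes pregnant during the study will be followed through the pregnancy outcome".

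**What counts as the study.** Section 3.1 names two periods. The first is 52 weeks of open-label treatment and the second is listed as "Safety follow-up period (at least 30 days". On completion, the same section adds: "Please note that this includes the safety follow-up visit/contact, whichever is later".

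**Contraception.** Under inclusion criterion 5 in section 4.1, a woman of childbearing potential "must agree to use TWO clinically acceptable methods of contraception during the study and 1 month following completion of the study".

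**Last test and last contact.** Table S-1 and Table 6–1 place the final pregnancy test at Visit 9 (EOT/ET). For the telephone call, 6.4 says: "Subjects should have the following completed at least 30 days after last dose of study drug". It then lists two items, concomitant medications and AEs. The Visit 10 column of Table S-1 adds background antidepressant adherence. Neither place has a pregnancy question or test. Section 7.1.1 states: "Pregnancy will not be considered an AE, but if it occurs, it will be reported on a pregnancy form".

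**Men.** Section 7.4.3.1 covers a father's "exposure to a medicinal product before or during his partner" (the sentence goes on to the partner's pregnancy) and gives no closing date.

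**The concern.** There are two separate weaknesses.

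The first is detection. A conception shortly before the last dose is exposed to the drug, but it may be too recent to show on the Visit 9/ET test. The one later contact does not ask about pregnancy, and its AE item does not call for it because pregnancy is not an AE. A reportable pregnancy can therefore pass through the closing procedures without any required step that looks for it.

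The second is scope. The contraception requirement treats the month after study completion as a period that matters. If completion includes the follow-up contact, as 3.1 says, that month begins after the last contact and lies outside the wording of 7.4.3. A site that learned of a pregnancy conceived then would have no instruction in 7.4.3 to report it or follow it to outcome.

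At stake are subject safety and the completeness of the exposed-pregnancy record. No endpoint or statistical figure is affected.

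**Working it through.** **1. Are the 30 days after the last dose part of the study?** Inputs from 3.1: 52 weeks of treatment, follow-up of at least 30 days, and participation of about 56 weeks.

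(52 × 7 + 30) / 7 = 394 / 7 = 56.3 weeks

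This reproduces the stated figure. The 30 days are inside the study, so conceptions in them fall under 7.4.3.

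**2. When are tests done?** Table S-1 has tests at Weeks 0, 4, 8, 12, 16, 28, 40 and 52/ET. The gaps are 28, 28, 28, 28, 84, 84 and 84 days, and there is no test after that.

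**3. How much falls after the last test can detect it?** The documents give no lag from conception to a positive urine test. I assume 10 to 21 days, a constant conception hazard, and a last test on the last-dose day. With T days on drug:

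- Share of on-drug conceptions too late for the last test = lag / T
- Share of conceptions up to 30 days after the last dose = (lag + 30) / (T + 30)

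| Subject | lag / T | (lag + 30) / (T + 30) |
|---|---|---|
| 52-week completer, T = 364 | 10/364 = 2.7% to 21/364 = 5.8% | 40/394 = 10.2% to 51/394 = 12.9% |
| Stopped at Week 16, T = 112 | 10/112 = 8.9% to 21/112 = 18.8% | 40/142 = 28.2% to 51/142 = 35.9% |

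The Week 16 row is an example. Early exits did occur: SAP 3.6 says the study was stopped early and the remaining subjects discontinued.

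**4. Sensitivity to the timing of the last test.** If it is done 7 days after the last dose, the completer's on-drug share falls to (10 − 7)/364 = 0.8% to (21 − 7)/364 = 3.8%. In the other direction, 4.4.1 makes Visit 9/ET a matter of reasonable effort after early discontinuation. Without that test, a subject who leaves after Week 16 could have gone up to 84 days on drug since her last test, plus the 30 days to the call.

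**5. What could a question at the call find?** At a call 30 days after the last dose, every on-drug conception is at least 30 days old, which is longer than the assumed lag. Of the 30 post-dose days, conceptions in roughly the first 30 − 21 = 9 to 30 − 10 = 20 days would also be old enough to be known.

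**6. Where does the contraception month fall?** There are two main readings of completion:

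- *It includes the follow-up contact (3.1).* The month starts after Visit 10. It is outside 7.4.3 and no contact is scheduled in it.
- *It means end of treatment.* The month roughly coincides with the follow-up period. It is inside 7.4.3 but still not asked about.

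Section 3.1 supports the first reading. It also ties completion, even for an individual, to the date the final subject at any site finishes, so the window has no clear end for one woman.

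**The case against.** The strongest reply is that the reporting rule already does most of what is needed. A reader might infer that late-dosing and 30-day conceptions are outside 7.4.3 and so are missed. The documents do not support that: follow-up is part of the study, and the 24-hour clock runs from discovery with no cut-off. Section 7.4.1 has the investigator ask a nonspecific question about changes since the last visit, and Visit 10 includes AE assessment, so a pregnancy could be volunteered. Section 7.4.2 follows subjects for 30 days for other reportable information as well as SAEs. All of this stands, and for these conceptions the gap is one of detection. What remains is that none of these provisions tells the site to ask about pregnancy.

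A reader might also treat the contrast with men as proof that the female rule is defective. It is not proof. Section 7.4.3.1 defines a type of exposure and sets no observation window. The contrast only shows that the two rules are framed differently.

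The percentages are open to fair criticism. The lag is assumed, the result moves with the test date, and they say nothing about the month after the call. Two contraceptive methods are required, so the number of pregnancies may be very small. The consent pages and the Pregnancy form are not available for review, so what subjects are told about reporting cannot be judged. Finally, the study has been stopped, which limits the practical effect of a change here.

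**Conclusion.** The point holds in two limited parts.

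- **Detection.** Conceptions late in dosing or in the 30 days after the last dose are reportable but may go undetected, because no required step after Visit 9/ET looks for them. For a 52-week completer, 2.7% to 5.8% of on-drug conceptions come too late for the last test. This rests on an assumed lag of 10 to 21 days, a constant hazard, and a last test on the last-dose day.
- **Scope.** Only the contraception month after study completion lies outside 7.4.3, and this depends on completion including the follow-up contact, as 3.1 says.

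A reader might infer a number of missed pregnancies from these percentages. The documents cannot support one, since they give neither a conception rate nor the number of women of childbearing potential. A reader might also expect a Visit 10 question to cover the contraception month. It cannot, because the call comes before that month starts.

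This is an inexpensive improvement to safety ascertainment. It changes no analysis.

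**What to change.** 1. Add one question on pregnancy to the Visit 10 call, in 6.4 and in the Visit 10 column of Table S-1. Ask it of female subjects of childbearing potential, and ask male subjects about their partners. No new test or visit is needed.
2. Reconcile 3.1, 4.1 (criterion 5) and 7.4.3. State the start and end of the female reporting window for the individual subject, and align it with the contraception period the sponsor intends. A conception after the call is then reportable, and followed to outcome, when the site learns of it.

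The cost is protocol wording, one question on a call already made, and a few more Pregnancy forms.
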